Compared to the selection of all PI-RADS ≥ 4 lesions (high sensitivity, poor specificity), the combined ^{18}F -choline PET/MRI model resulted in an improvement of the specificity by +38% with only a modest reduction in sensitivity (-10%). Implementation of this rule would have reduced the number of targeted lesions for biopsy by roughly 50% (from 51 to 25), exemplifying the cost-saving potential of a PET/MRI strategy. Given that ^{68}Ga -PSMA and ^{18}F -choline have different molecular targets (^{68}Ga -PSMA has higher specificity for PCa than ^{18}F -choline), and that the ^{18}F -choline trial investigated a high-risk patient population, these ^{18}F -choline results are not directly transferable to the use of ^{68}Ga -PSMA PET/MRI such as is being investigated in this proposal. Furthermore, any future ^{68}Ga -PSMA PET/MRI rule would likely be constructed differently. For sample size estimates in this trial, we therefore project conservatively that the sensitivity of mpMRI would minimally increase (by 2%, mainly from correctly identifying significant cancers rated as PI-RADS 3), while the specificity would increase by only 15%. Given the known superiority of ^{68}Ga -PSMA over ^{18}F -choline, as well as the known increase of PSMA-expression with increasing aggressiveness (Gleason scoring), we have no reason to assume that the performance of ^{68}Ga -PSMA would be inferior to ^{18}F -choline for the identification of significant PCa. As a result, these sample size estimates are quite conservative.

In conclusion, we are confident that the necessary number of subjects can be recruited with sufficient prevalence of significant PCa in this trial. The inclusion criteria will ensure a sufficient potential for positive imaging findings with ^{68}Ga -PSMA PET/CT, and a very high probability of successful targeting with image-guided biopsy.¹⁶

Table 1. Estimated incidence of Gleason 3+3 vs. $\geq 3+4$ vs. benign biopsy results in the trial population

Maximum PI-RADS risk score per subject	Number of subjects (%)	No prostate cancer Benign %	Total maximum grade Gleason = 3+3 %	Total maximum grade Gleason $\geq 3+4$ %
3	30	16 (53%)	10 (33%)	5 (17%)
4	49	9 (27%)	13 (27%)	26 (53%)
5	21	1 (5%)	3 (14%)	17 (81%)
Total (N)	100	26	26	48

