12.1 Sample size determination

Sample size calculation was made for the primary objective only. We assess potential differences between the predictive performances of the two models (1) and (2), while maintaining ethical and economic considerations. We consider the positive likelihood ratio (positive LR) as a performance measure, which is defined by a ratio of sensitivity to 1-specificity. A higher positive LR means greater predictive information of positive test results irrespective of disease prevalence. Based on preliminary data obtained from mpMRI, we assume that the sensitivity and specificity of model (1) are both given by 0.789. For model (2), we assume conservatively that the sensitivity will be increased by 0.02 (2%) and that the specificity would improve by 0.15 (15%). In this scenario, the positive LR of model (1) is given by 3.74 and the positive LR of model (2) is calculated as 5.02. In order to detect the 1.28 difference in positive LR between the two models, we need at least 100 subjects, including at least 38 of 100 subjects with a histological diagnosis of significant PCa. The sample size was estimated as described in the literature.⁵⁸

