12.2 Significance Level

All statistical tests will use a 0.05 significance level.

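### The Section 12.1 size condition sets a minimum only for men with significant PCa, so it does not secure power for the LR+ difference, which depends mainly on men without it

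*Combined protocol and SAP*

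**What the plan says.** Section 12.1 takes LR+ as the performance measure, "which is defined by a ratio of sensitivity to 1-specificity". For mpMRI alone, "we assume that the sensitivity and specificity of model (1) are both given by 0.789". For the combined model it adds 0.02 to sensitivity and 0.15 to specificity, and reports that "the positive LR of model (1) is given by 3.74 and the positive LR of model (2) is calculated as 5.02". For that difference of 1.28, "we need at least 100 subjects, including at least 38 of 100 subjects with a histological diagnosis of significant PCa". Power is not stated, and the method is given only by citation: "The sample size was estimated as described in the literature". Section 12.2 adds that "All statistical tests will use a 0.05 significance level".

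Table 1 in Section 12 projects, for 100 men, 48 with Gleason 3+4 or higher, 26 with Gleason 3+3 and 26 benign. That is 48 with significant PCa and 52 without. The text just before the table concludes that "we are confident that the necessary number of subjects can be recruited with sufficient prevalence of significant PCa in this trial". It does not mention the number of men without significant PCa.

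**The concern.** The denominator of LR+ is the false-positive rate, which is estimated only in men without significant PCa. The projected gain is also almost all in specificity. Yet the written condition places no lower limit on that group, other than what remains of the total. With 100 men, each additional cancer removes a man from the group that mostly determines precision. An adequacy check based on the number of cancers therefore cannot show a shortage where it matters most for the primary outcome. The investigators could meet the condition and report the trial as adequately sized when its power to separate the two LR+ values had fallen.

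**Working it through.** **Inputs.** From Section 12.1: model (1) sensitivity and specificity 0.789; model (2) sensitivity 0.809; LR+ 3.74 and 5.02; at least 100 men, at least 38 with significant PCa. From Table 1: 48 with, 26 + 26 = 52 without. From Section 12.2: alpha 0.05. Assumed here: a two-sided test of equal LR+, and a between-test correlation ranging from independence to maximum overlap.

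**The plan's own figures.** LR+ for model (1) reproduces: 0.789/0.211 = 3.74. For model (2), the increments as worded give specificity 0.939 and LR+ 0.809/0.061 = 13.26. The printed 5.02 corresponds to specificity 0.839 (0.809/0.161 = 5.02), a gain of 0.05. Both versions are carried below. The size of 100 does not reproduce for the stated difference: with 38% diseased, independent readings and an assumed 80% power, about 1,417 men are needed for 5.02 and about 158 for 13.26.

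**Formula.** Let n1 be men with and n0 men without significant PCa, with s the sensitivities and f the false-positive rates. Then

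Var[log(LR2/LR1)] = A/n1 + B/n0,

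A = (1−s1)/s1 + (1−s2)/s2 − 2·cov/(s1·s2), and B is the same expression in f. The covariance is zero under independence. At maximum overlap the last term is 2(1/s2 − 1) in A and 2(1/f1 − 1) in B.

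- A, independent: 0.267 + 0.236 = 0.5035. At maximum overlap: 0.5035 − 0.4722 = 0.0313.
- B for 5.02, independent: 3.739 + 5.211 = 8.950. At maximum overlap: 8.950 − 7.479 = 1.472.
- B for +0.15, independent: 3.739 + 15.393 = 19.133. At maximum overlap: 19.133 − 7.479 = 11.654.
- Effect: ln(5.025/3.739) = 0.2955, or ln(13.262/3.739) = 1.266.

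**Share of variance.** At 38/62 for 5.02 with independent readings, A/38 = 0.0133 and B/62 = 0.1444. The men without significant PCa contribute 0.1444/0.1576 = 91.6%. The share is 96.6% at maximum overlap, and 95.9% to 99.6% for +0.15. At 48/52 it is higher in every case.

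**Power, two-sided 0.05, 100 men** (with/without significant PCa):

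| Scenario | 38/62 | 48/52 | 80/20 |
|---|---|---|---|
| LR+ 3.74 vs 5.02, independent | 11.5% | 10.6% | 7.2% |
| LR+ 3.74 vs 5.02, maximum overlap | 47.0% | 41.2% | 19.2% |
| Specificity +0.15, independent | 60.7% | 53.9% | 25.2% |
| Specificity +0.15, maximum overlap | 83.0% | 76.1% | 38.1% |

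All three splits satisfy the written condition.

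**Which group adds power.** Start from 38/62 with +0.15 and independent readings (60.7%). Ten more men with significant PCa raise power to 61.1%; ten more men without it raise power to 66.9%.

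**Checks.** A simulation of 40,000 runs per setting gave the same direction. For 38/62 and 48/52 it gave 10% and 9% (5.02, independent), 42% and 31% (5.02, nested), 65% and 57% (+0.15, independent), and 98% and 94% (+0.15, nested). The levels differ from the formula, most of all for nested readings with +0.15, so the table shows direction and approximate size, not exact power. Taking accuracies from Table 1 for PI-RADS 4 or higher (43/48 = 0.896 and 26/52 = 0.50) with the same increments gives 38.5% at 38/62 and 34.3% at 48/52, independent.

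**The case against.** A reader might infer that the floor sits on the wrong group and should be removed. The documents do not support that. Section 12.1 also sets a minimum for the total. Sensitivity is part of the primary objective in Section 5, and Section 12.5.2 reports it with 95% confidence intervals whose precision depends only on men with significant PCa. A floor there also matters for LR+: for 5.02 with independent readings, 38 cancers cap power at about 73% however many men without cancer are added.

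A reader might also infer that the plan needs 62 men without significant PCa and that Table 1 falls short at 52. The figure 62 is only 100 − 38; the plan does not state it as a requirement, and the formula is not shown. One precision calculation gives 38 per group: (1.96/1.266)² × (0.236 + 15.393) = 37.5. That may be coincidence, and it uses 13.26, not 5.02, but under it 52 would be ample.

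Two further points stand. The planned model in Section 12 is at lesion level, and men with cancer can contribute negative lesions. The team's earlier choline trial had 30 positive and 60 negative lesions in 56 men, although the plan says those results do not transfer directly. Section 12 also lists a test of the PET coefficient ahead of the LR+ comparison, and the best split for that test need not be the same. Neither point supplies the missing minimum for the measure on which 12.1 bases its size.

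**Conclusion.** The point holds as a gap in the size statement: the condition in 12.1 does not secure detection of the 1.28 difference, because it leaves unprotected the group that supplies about 92% or more of the variance. At Table 1's split the cost relative to 38/62 is about 1 to 7 points of power by formula, and 1 to 11 in the simulation. The large losses need a split such as 80/20, which the plan does not project, so these figures do not show that the trial is expected to lose most of its power. Nor do they show that 100 men are enough: at the stated 5.02, power is below 50% at either 38/62 or 48/52 in every variant above.

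The direction was the same in every variant tried. The absolute values rest on the assumed correlation, a two-sided test of equal LR+, and subject counts as a proxy for lesions. The conflict between 5.02 and 13.26, and the absence of a stated power and formula, are larger faults in 12.1, but resolving them would still leave the condition one-sided.

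**What to change.** In Section 12.1, first make the model (2) accuracies and the LR+ of 5.02 agree. Then recompute at Table 1's 48/52 split with a stated between-test pairing assumption, and print the resulting power or detectable LR+ difference in place of the present claim. Keep a minimum for men with significant PCa, justified by the precision of sensitivity, and add a minimum for men (or lesions, to match the model) without it. In Section 12, report the expected 52 men without significant PCa beside the prevalence statement. Do not describe 62 as a requirement, and do not assert that 100 is adequate until the recalculation is done.

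The cost is one recalculation and a few sentences. The stated detectable difference will become less favourable.

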12.2 Significance Level

All statistical tests will use a 0.05 significance level.

12.3 Rules for excluding subjects from analysis

All dosed subjects will be included in the analyses unless otherwise specified. The PI will make any decisions regarding whether any subjects or any individual values belonging to a subject who violates the protocol will be excluded from the evaluations when the protocol violation is considered to have a negative impact on the scientific aspects and interpretation of the study results. The PI will also make a decision whether recruited

subjects with incomplete assessments will be substituted with additional subjects beyond the total recruitment goal.

12.4 Withdrawal from assessment and replacement

Subjects who show major protocol deviations, e.g. deviations leading to the loss of essential data for the evaluation of the diagnostic efficacy can be withdrawn and replaced. The decision regarding withdrawal and replacement will be made by the principal investigator consulting with the study team.

12.5 Analysis Plan

12.5.1 Analysis Population

Patients with histopathology correlates will be analyzed for the primary aim. All remaining patients will be analyzed for the secondary endpoints.

12.5.2 Analysis of Primary Endpoints

PET images will initially be interpreted by a board certified nuclear medicine physician or a board-certified radiologist experienced in reading PET at the time of the imaging study at Michigan Medicine. Upon request, case report forms and coded ⁶⁸Ga-PSMA PET/CT imaging data will be provided to the FDA for review.

Intraprostatic lesions identified by mpMRI as PI-RADS 3-5 will be graded visually on a two-point scale as either positive or negative for elevated ⁶⁸Ga-PSMA uptake relative to prostatic gland uptake (0=Negative or 1=Positive).

Any focal intraprostatic elevated ⁶⁸Ga-PSMA uptake relative to prostatic gland that was not identified by mpMRI (as PI-RADS 3-5) but was targeted at biopsy will also be evaluated visually as either positive or negative (0=Negative or 1= Positive).

All subjects with histopathology correlates will be analyzed for the primary aim. Sensitivity and specificity, positive and negative predictive values, and accuracy (along with the corresponding two-sided 95% confidence intervals) will be determined on a per-subject and per-lesion basis for ⁶⁸Ga-PSMA-11 PET and mpMRI regarding the detection of Gleason \geq 3+4 cancer. Standard reference of truth is histopathology from all individual biopsy cores, targeted and standard cores.

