5 STUDY OBJECTIVES AND PURPOSE

The primary study aim is the prospective comparison of standard-of-care mpMRI vs. combined ⁶⁸Ga-PSMA PET and mpMRI (⁶⁸Ga-PSMA fusion PET/MRI) for the detection and risk-stratification of clinically significant primary PCa.

Following (clinical) mpMRI and (research) ⁶⁸Ga-PSMA PET/CT imaging, we will perform targeted and standard 12-sample prostate biopsies. Biopsy targets will be defined from mpMRI and ⁶⁸Ga-PSMA PET; mpMRI interpretation will be done in accordance with PI-RADS v2.

Primary objective: We will determine the sensitivity and specificity of mpMRI alone and mpMRI in combination with ⁶⁸Ga-PSMA PET (i.e., fusion PET/MRI) for the detection of primary Gleason $\geq 3+4$ PCa. Primary outcome measure: determination whether the positive likelihood ratio (LR) for ⁶⁸Ga-PSMA PET-MRI is at least 1.28 greater than that of standard-of-care mpMRI. Reference standard will be pathology defined as targeted plus standard prostate biopsy, and prostatectomy, when available.

Secondary objective: We will determine the safety of ⁶⁸Ga-PSMA. We will also determine frequency and location of ⁶⁸Ga-PSMA positive lesions, such as potential extra-prostatic extension, lympho-nodal and/or distant metastatic disease positive on ⁶⁸Ga-PSMA but not identified by conventional (standard) imaging. While histological verification would be desirable, the decision for or against tissue verification will depend on clinical decisions making only, and not be required due to study participation.

Exploratory objective: We will evaluate whether radiomics classifiers (obtained from mpMRI and ⁶⁸Ga-PSMA identified targets) could improve identification and risk stratification of significant PCa. Reference standard will be pathology defined as targeted plus standard prostate biopsy, and prostatectomy, when available.

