9.2.1 Target identification

In-vivo imaging (PET and/or MRI) will be reviewed by participating investigators for intraprostatic lesions suspicious for significant prostate cancer. After registration of imaging data to the T2-weighted MRI, the responsible radiologists ([name] and [name], or designees) will determine potential target areas for image-guided (targeted) prostate biopsy within the T2-weighted MRI (reference space). Candidate targets are the known PI-RADS 3-5 lesions, where higher PI-RADS scores will be preferentially selected. Any PI-RADS 5 lesion will be targeted for biopsy (unless there are more than 3). ⁶⁸Ga-PSMA positive lesions not identified by mpMRI as PI-RADS 3-5 will be considered as well. Currently available preliminary retrospective data suggest that a suitable threshold for ⁶⁸Ga-PSMA positivity (defining significant disease) would be ≥ 2 standard deviations above prostate background.³²

To limit the burden to the subject, no more than 3 target locations will be selected for biopsy. If more than 3 targets are present (from both PET and/or MRI), the most suspicious 3 are selected; in case of a tie, the largest will be selected. The selected targets are then transferred to the navigated ultrasound workstation used for targeted prostate biopsies.

Radiomics analysis results will not be used to identify targets for prostate biopsies.

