9.2.2 Prostate biopsy procedure

Prostate cancer subjects recruited for this study are expected to receive tissue sampling for clinical (diagnostic) purposes. Accordingly, all subjects already had a prior mpMRI indicating presence of a prostate lesion potentially representing prostate cancer (PI-RADS 3-5).

Targeted (fusion) prostate biopsies based on TRUS-MRI guidance are routine clinical practice at Michigan Medicine. While typically all biopsy targets are sampled, it is at the discretion of the physician performing the prostate biopsy which of the selected targets are biopsied. Typically, a total of 2 sample cores are obtained from each target. However, to account for biopsy cores missing the target area the exact number of biopsy cores obtained from a given target is at the discretion of the physician performing the prostate biopsy procedure.

The histological results of the biopsy will be compared to PI-RADS scores and respective visual and quantitative radiotracer uptake measures.

Patient monitoring after the prostate biopsy procedure will be done according to standard of care. The patient will receive specific instructions and guidance for minor and more serious adverse effects.

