9.2.5 Image interpretation and correlation with standard of truth

PET and MR imaging will be assessed visually. Abnormalities found on MRI and ⁶⁸Ga-PSMA PET will be selected as targets for image-guided biopsies.

Once prostate biopsies are obtained, the location of each biopsy is retrospectively associated with a matching region on pre-biopsy imaging (facilitated via image co-registration) and semi-quantitative PET data are obtained and compared with the standard of truth (Gleason score histology). Accordingly, we will determine whether a selected target was true positive, false positive, true negative or false negative on imaging (MRI and ⁶⁸Ga-PSMA PET) relative to pathological proof. Please note that the location (in 3D space) of a given biopsy core is known from ALL biopsies, whether obtained as standard or targeted core. This is possible because the navigated ultrasound workstation (i.e. UroNav, Invivo) used will record the biopsy core location (trajectory and core length within the gland) in 3D for all cores obtained ^{55,56}.

Accordingly, the sensitivity and specificity for the detection of low-grade (Gleason 3+3) and significant PCa (Gleason \geq 3+4) is determined for both modalities, ⁶⁸Ga-PSMA PET (based on uptake measures) and mpMRI (based on PI-RADS scores).

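### A PET-only focus is scored only if it was targeted, while PI-RADS 3-5 lesions are graded without that condition, so per-lesion PET/MRI specificity depends on target selection and is probably flattered

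*Combined protocol and SAP*

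**What the plan says.** Section 12.5.2 (Analysis of Primary Endpoints) sets two entry rules. For mpMRI lesions: "Intraprostatic lesions identified by mpMRI as PI-RADS 3-5 will be graded visually on a two-point scale". For PET foci that mpMRI did not rate PI-RADS 3-5, the focus is included if it is elevated relative to the gland "but was targeted at biopsy will also be evaluated visually as either positive or negative". The same section takes all individual cores, targeted and standard, as the reference standard and plans accuracy measures per subject and per lesion.

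What becomes a target is settled earlier. In section 9.2.1, "no more than 3 target locations will be selected for biopsy", counted over PET and MRI together. When there are more, the three most suspicious are kept. Higher PI-RADS scores are preferred, and PET-only foci are candidates to be considered. In section 9.2.2, "it is at the discretion of the physician performing the prostate biopsy which of the selected targets are biopsied".

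The protocol also samples outside the targets. In section 5, "we will perform targeted and standard 12-sample prostate biopsies", and in section 9.2.5, "the location (in 3D space) of a given biopsy core is known from ALL biopsies, whether obtained as standard or targeted core". Section 9.2.5 matches each biopsy to a region on imaging, then states its classification in terms of targets: "we will determine whether a selected target was true positive, false positive, true negative or false negative on imaging".

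**The concern.** The two entry rules differ. Suppose a PET-only focus is not targeted and a standard core passes through it and is benign. The histology exists, its location is known and it belongs to the reference standard, yet 12.5.2 does not score the focus. It would have been a false positive for PET. The same core through an untargeted PI-RADS 3-5 lesion at least meets a lesion that 12.5.2 has graded.

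Selection keeps the most suspicious targets, so the foci left out are likely to be the weaker ones, and weaker foci are more likely to be benign. Specificity is where the plan expects nearly all of the PET gain (section 12.1), and LR+ divides by 1 - specificity. A few omitted false positives can therefore move the primary measure noticeably.

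A separate gap concerns standard cores from regions negative on both scans. No rule says whether such a region is a per-lesion unit. The primary criterion is an absolute LR+ difference of 1.28, and that difference changes with how many such regions are counted.

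**Working it through.** **Inputs.** Section 12.1: sensitivity and specificity of mpMRI both 0.789; sensitivity of PET/MRI 0.789 + 0.02 = 0.809; stated LR+ 3.74 and 5.02. Table 1: 26 + 26 = 52 subjects without Gleason ≥3+4 cancer and 48 with it. Table 1 counts subjects; they stand in for lesions here only because the plan gives no lesion counts.

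**The plan's own figures.** LR+ = sensitivity / (1 - specificity).
- mpMRI: 0.789/0.211 = 3.74, as stated.
- PET/MRI: the stated 5.02 corresponds to specificity 0.839 (0.809/0.161 = 5.02). The specificity gain written in section 12.1, 0.15, gives 0.939 and 0.809/0.061 = 13.26. That discrepancy is a separate matter, but it affects the illustration, so both values are carried.

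**Restoring k benign untargeted PET-only foci.** Assume that each counts as positive for PET/MRI and negative for mpMRI. False positives among 52 negatives are 52 × 0.211 = 10.97 for mpMRI and, on the stated 5.02, 52 × 0.809/5.02 = 8.38 for PET/MRI. Then:

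mpMRI LR+ = 0.789 × (52 + k)/10.97

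PET/MRI LR+ = 0.809 × (52 + k)/(8.38 + k)

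| k | mpMRI | PET/MRI | Difference |
|---|---|---|---|
| 0 | 3.74 | 5.02 | 1.28 |
| 1 | 3.81 | 4.57 | 0.76 |
| 2 | 3.88 | 4.21 | 0.33 |
| 3 | 3.96 | 3.91 | -0.05 |

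With specificity 0.939, PET/MRI starts with 52 × 0.061 = 3.17 false positives. The difference is then 9.52 at k = 0, and 6.47, 4.56 and 3.25 at k = 1, 2 and 3: smaller each time, but with no reversal. With 62 negatives (100 - 38, section 12.1) and specificity 0.839, the difference is 1.29 unrounded at k = 0, 0.46 at k = 2 and -0.42 at k = 5.

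**Restoring a cancer instead.** Some omitted foci may be true positives. Adding one to the 48 diseased units gives sensitivity (0.809 × 48 + 1)/49 = 0.813 for PET/MRI and 0.789 × 48/49 = 0.773 for mpMRI. LR+ becomes 5.04 and 3.66, a difference of 1.38. On the stated LR+ values, an omitted cancer costs PET/MRI 0.10 and an omitted benign focus gains it 0.52.

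**Regions negative on both scans.** Adding d diseased and h non-diseased units to D and H multiplies both LR+ values by [D/(D + d)] × [(H + h)/H]. If benign regions double the negatives (d = 0, h = H), LR+ becomes 7.48 and 10.04. The difference rises from 1.28 to 2.56, and the ratio stays at 5.02/3.74 = 1.34.

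**The case against.** The strongest reply is that the plan's sampling is better than this suggests. Standard cores are taken in everyone, matched to imaging, and count in the per-subject analysis. Section 9.3.2 also compares histologically verified cancers with co-localized findings on both scans. A reader might infer that regions negative on both scans never enter the evaluation. The documents do not support that: what is missing is a per-lesion rule.

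A reader might also infer that PET false positives in general drop out. They do not. Benign PET-positive PI-RADS 3-5 lesions and benign targeted PET-only foci remain false positives; only untargeted PET-only foci are lost.

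Nor is selection confined to PET. The cap and the operator's discretion apply to mpMRI lesions too, section 9.2.5 classifies selected targets of either kind, and the model in section 12 refers to biopsied lesions. Being graded under 12.5.2 does not guarantee an mpMRI lesion an accuracy classification, so the net direction is not proved.

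The number of omitted foci may be small. The earlier choline trial had 90 mpMRI lesions in 56 subjects, about 1.6 each against a cap of three. Section 9.2.2 says targets are usually all sampled, and section 11.2.3 expects the main effect to come from rescoring known lesions.

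These points limit the claim. They do not remove the explicit targeting condition in 12.5.2, which leaves located reference-standard histology unused for one kind of lesion.

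**Conclusion.** The point stands in a limited form. Section 12.5.2 makes scoring of PET-only foci conditional on targeting, and grading of PI-RADS 3-5 lesions is not conditional. The likely effect is to favour PET/MRI specificity, because the most suspicious targets are kept. The size is unknown.

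The illustration shows sensitivity, not a forecast. It rests on an assumed k, on subject counts used as lesion counts, and on each restored focus being called positive by the combined model, which a PET-positive focus below PI-RADS 3 need not be. A reader might infer from the k = 3 row that three such foci would reverse the primary result. That holds only with 52 negatives and LR+ 5.02, and it disappears at the specificity gain that section 12.1 actually states.

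The missing rule for regions negative on both scans is a gap in definition. It scales both LR+ values equally, so it changes the absolute difference and not the ratio, and does not itself favour PET.

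**What to change.** - In section 12.5.2, delete the targeting condition (the first five words of "but was targeted at biopsy will also be evaluated visually as either positive or negative").
- Score every PET-positive intraprostatic focus and every PI-RADS 3-5 lesion by one rule: against any targeted or standard core whose recorded 3D track crosses it. Align the classification sentence in section 9.2.5 with that rule.
- Fix the imaging reads and the core-to-lesion matching rule before histology is known. This matters because the study is unblinded (section 8.3) and the matching is retrospective (section 9.2.5).
- Report lesions crossed by no core as unverified, separately for PET-only foci and mpMRI lesions.
- If standard-core regions negative on both scans are added, do so as a sensitivity analysis and compare the modalities by the LR+ ratio (1.34 on the stated values). Adding them while keeping the 1.28 difference would make that threshold depend on how the gland is divided.

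The cost is a wording change and extra co-registration of cores that are already taken and located; no extra biopsies are needed. The drawbacks are some registration error and weaker verification where a focus is judged from an incidental standard core.

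### Section 12.5.2 lets a focus that was targeted because it was PET-positive be graded PET-negative, with no rule that the call leading to biopsy is the one scored

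*Combined protocol and SAP*

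**What the plan says.** Section 9.2.1 takes the known PI-RADS 3-5 lesions as candidate targets and adds one further class: PSMA "positive lesions not identified by mpMRI as PI-RADS 3-5 will be considered as well". The threshold it mentions for positivity, as a suggestion from retrospective data, is at least 2 "standard deviations above prostate background".

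Section 12.5.2 then grades uptake for the primary analysis. PI-RADS 3-5 lesions "will be graded visually on a two-point scale as either positive or negative for elevated" uptake, judged against the prostatic gland. The next paragraph concerns focal uptake that is already described as elevated against the gland, "that was not identified by mpMRI (as PI-RADS 3-5) but was targeted at biopsy". It says that uptake which "was targeted at biopsy will also be evaluated visually as either positive or negative", again with 0 for negative and 1 for positive.

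From these grades, 12.5.2 derives PET sensitivity, specificity, predictive values and accuracy, per subject and per lesion. Section 9.2.5 matches imaging to histology after the biopsy and states that "we will determine whether a selected target was true positive, false positive, true negative or false negative on imaging". Section 8.3 rules out blinding. Section 12.5.2 places the initial PET interpretation at the time of imaging but does not say when the 0/1 grade is assigned. Section 9.3.3 adds a separate visual score from 0 to 3 for every target volume.

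**The concern.** A PET-only focus is by definition negative on mpMRI at the PI-RADS 3 cut. Graded 0, it would be a target that neither test called positive, although the plan gives no other route to a targeted core. The call that sent the man to an extra core would then differ from the call scored as the test result.

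PET-only foci are the lesions through which PET can add false positives that mpMRI alone would not have produced. If some of those calls can be withdrawn in the analysis, the false-positive cost of PET is understated. Conversely, withdrawing the call on a focus that proves to be significant cancer denies PET a detection that it made. The plan neither says which call counts when the two differ nor fixes the grade before the histology is known.

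**Working it through.** **The two passages side by side.**

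1. Entry to the class (9.2.1 and 12.5.2): no PI-RADS 3-5 score, elevated PSMA uptake, targeted at biopsy.
2. Grading criterion (12.5.2, preceding paragraph on MRI lesions): 1 means elevated uptake relative to the gland.
3. The entry condition and the criterion for grade 1 are the same property. Read literally, grade 0 should be empty for this class, yet it is offered.
4. Effect of a 0 on the PET classification in 9.2.5:

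| Histology of the PET-only focus | Call that led to biopsy | Scored if graded 0 |
|---|---|---|
| Benign or Gleason 3+3 | false positive | true negative |
| Gleason 3+4 or higher | true positive | false negative |

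**The plan's own figure.** Section 12.1 defines LR+ = sensitivity / (1 − specificity).

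- Model (1): 0.789 / 0.211 = 3.74, as stated.
- Model (2) with the stated gains of 0.02 and 0.15: 0.809 / 0.061 = 13.26, not the stated 5.02.
- 5.02 is obtained with a specificity gain of 0.05: 0.809 / 0.161 = 5.02.

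That mismatch is a separate matter. I use 5.02 only as a yardstick because the 1.28 criterion is built on it. It belongs to model (2); the plan gives no planning LR+ for PET alone.

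**Size of a regrade.** The documents give no expected number of PET-only foci, so the number regraded, k, is an assumption. Moving k false positives to true negatives among n non-diseased units gives LR+ = 0.809 / (0.161 − k/n).

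- n = 62 (100 subjects minus the minimum of 38 diseased in 12.1; 62 × 0.161 ≈ 10 false positives): k = 1, 2, 3 gives 5.58, 6.28, 7.18. Two regrades are worth 6.28 − 5.02 = 1.26.
- n = 52 (26 + 26 in Table 1): k = 1, 2 gives 5.71, 6.60.
- n = 107 lesions. This is assumed from the choline trial in section 12: 90 lesions in 56 men is 1.61 per man, hence 161 lesions in 100 men, of which 60/90 are non-cancer. There are then 107 × 0.161 ≈ 17 false positives, and k = 3, 4 gives 6.08, 6.54. Each regrade moves specificity by 1/107 = 0.9 percentage points.

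The figures for 62 and 52 are upper bounds. They treat each focus as a man whose result flips, but every man enters with at least one PI-RADS 3-5 lesion, and his per-subject PET result flips only if no other lesion of his is PET-positive.

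**The opposite error.** With 38 diseased, one true positive turned into a false negative gives (0.809 − 1/38) / 0.161 = 4.86; with 48 diseased (Table 1) it gives 4.90. LR+ therefore reacts more to the false-positive side. With 38 and 62 units, one error of each kind gives 0.783 / 0.145 = 5.40, with sensitivity lower and specificity higher.

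**The case against.** The strongest reply is that 12.5.2 describes no second read and no reversal. It prints a two-point scale, and a focus defined as elevated would naturally score 1. That stands in part: the text permits a 0 and does not require one. A reader might infer that the plan as written converts PET false positives into true negatives. The documents do not support that, because it takes both a grade of 0 and histology below Gleason 3+4.

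A reader might also infer that the primary LR+ comparison is biased in favour of PET. That is not established either. The primary-objective paragraph of section 12 compares PI-RADS 3 or higher alone with the same plus PET, and does not say whether a focus without such a score enters model (2). Section 11.2.3 expects the main effect to come from modifying the MRI risk score. Nor is the direction fixed, since zeros on cancers count against PET.

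A third reply is that target selection may use the 2 SD threshold while 12.5.2 uses a visual read, so a focus could meet one and fail the other. This does not remove the conflict: 12.5.2 has already called the focus elevated relative to the gland before grading it, and no rule says which call is the test result.

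Finally, a fixed grade of 1 means that PET-only targets can never be PET-negative. That is true, but it describes how they were selected. PI-RADS 3-5 lesions can be targets whatever PET shows, so their 0/1 grade carries information. The timing of that grade is a separate matter that this change leaves open.

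**Conclusion.** The point holds as a gap in the scoring rule. Section 12.5.2 offers grade 0 to foci that are positive by definition, does not tie the grade to the call that led to biopsy, and does not fix it before histology in an unblinded study. PET sensitivity and specificity in 12.5.2 are directly exposed, mainly per lesion. A per-subject result changes only if the man has no other PET-positive lesion. The fusion LR+ changes only if PET-only foci enter model (2), which the plan leaves undefined.

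Sensitivity and specificity taken together favour PET only if the zeros fall mostly on histology-negative foci. The plan does not prevent that, but nothing in it says that it will happen. On assumed counts, two to four regraded false positives would shift LR+ by about as much as the 1.28 criterion. This shows how few foci matter; it is not an estimate of bias. The contradiction itself does not depend on the 5.02 base.

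**What to change.** In 12.5.2, replace the grading of PET-only targets with a rule such as: *A focus targeted because of PSMA uptake and not scored PI-RADS 3-5 is analysed as PET-positive (1), using the call recorded at target selection before biopsy; grade 0 is not available for these foci.* Apply the same call to the classification in 9.2.5. State that any later visual re-read, including the 0-3 score of 9.3.3, is a sensitivity analysis only. Keep the 0/1 grade for PI-RADS 3-5 lesions.

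The cost is one or two sentences and a dated record of the call at target selection. No procedure changes for the subject. PET specificity may look slightly worse.
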